**Table 6 Schedule of Assessments in Study E7080-G000-230 – Extension Phase**

Phase	Extension a	
Period	Treatment Period a	Follow-up Period
Visit	98	99
Cycle	Cycle X +1 and beyond	Off-Tx Visit
Day	1	

- r. Survival data will be collected every 3 months for up to 2 years as per the protocol. All anticancer therapies will be collected.
- s. Concomitant medications will be recorded throughout the study and for 30 days after last dose. All anticancer therapy will be recorded until time of death or termination of Survival Follow-up.
- t. All AEs, including SAEs will be recorded from the date of signed informed consent, throughout the study, and for 30 days after last dose. SAEs irrespective of relationship to study treatment must be reported as soon as possible but not later than 24 hours.

Table 7 presents the schedule of procedures/assessments for the Optional Lenvatinib Crossover Treatment Phase of the study.

**Table 7 Schedule of Assessments in Study E7080-G000-230 – Optional Lenvatinib Crossover Treatment Phase**

Phase	Baseline a	Optional Lenvatinib Crossover a						
		Treatment Period					Follow-up Period	
Visit	1	2+						
Cycle		1		2		3 and beyond	Off-Tx Visit	
Day	-1	1	8	15	1	15	1	
Procedures/Assessments								
Review eligibility b	X							
Lansky Play/Karnofsky PS Score c	X	X			X		X	X
Physical Examination d	X	X		X	X	X		X
Vital Signs e	X	X	X f	X	X	X		X
12-lead ECG g	X	X			X			X
ECHO or MUGA scan h	X	Performed every 16±2 weeks following first dose of study drug, or sooner if clinically indicated						X
Clinical chemistry and hematology i	X			X	X	X		X
Urine dipstick test j	X			X	X	X		X
Pregnancy test k	X				X		X	X
Study treatment l		Lenvatinib±chemotherapy						
Palatability Questionnaire m		X						
HRQoL	X	HRQoL will be collected at Baseline, C2D1, C3D1, and Week 18						
Tumor assessment: CT/MRI n	X	Tumor assessments may be performed as clinically indicated per the institutional guidelines (but no less frequently than every 12 weeks), following the prevailing local standard of care.						
Brain CT/MRI o		Brain CT/MRI scans may be performed as clinically indicated as per the institutional guidelines, following the prevailing local standard of care.						
Height p	X	X				X	X	X
Tanner Stage q	X						X	X
Survival r		X						X
Concomitant medications s	X	Throughout						X
AEs/SAEs t	X	Throughout						X

AE = adverse event, CT = computerized tomography, ECG = electrocardiogram, HRQoL = Health-Related Quality of Life, ICL = imaging core laboratory, MRI = magnetic resonance imaging, MUGA = multiple-gated acquisition, PD = disease progression, PS = performance status, SAE = serious adverse event.

a. Baseline assessments (except ECG, MUGA, and Tumor scans) may occur within 72 hours prior to C1D1. For subjects in Arm B only: subjects may be eligible for additional treatment with lenvatinib ± chemotherapy following disease progression. Note: subjects may only receive a maximum of 5 cycles of chemotherapy for the duration of the study.

Optional crossover treatment must be initiated within 30 days of documented disease progression. Please see [Section 9.1.4](#) of the protocol for further details.

- b. Subjects should meet all of the safety parameters listed in the inclusion criteria and none of the safety parameters listed in the exclusion criteria. If required locally, written informed consent will be obtained prior to assessment for Optional Lenvatinib Crossover treatment.
- c. A Lansky play score or Karnofsky performance status score will be obtained at Baseline, Day 1 of every cycle, and at the Off-treatment visit.
- d. A comprehensive physical examination (including a neurological examination) will be performed at Baseline, C1D15, C2D1, C2D15, Day 1 of each subsequent cycle, and at the Off-treatment Visit. A symptom-directed physical examination will be performed on C1D1 and at any time during the study, as clinically indicated.
- e. Assessments will include vital signs (resting BP, HR, RR, and body temperature) and weight. Blood pressure that is consistently above the 95th percentile for sex, age, and height/length for subjects <18 years old; or BP  $\geq$ 140/90 mmHg for subjects  $\geq$ 18 to 25 years old requires further evaluation. Refer to hypertension management guidelines in [Section 9.4.1.1.2](#).
- f. On Cycle 1 Day 8, subjects will have a telephone or clinic visit to assess for the development of early toxicity. Subjects will be provided with a BP cuff to monitor BP at home or can have the measurement done by a local healthcare provider, and will report the C1D8 measurement at telephone contact. An unscheduled visit can occur prior to C1D15 if deemed necessary by the investigator.
- g. Single 12-lead ECG. Baseline ECG may be performed within 28 days prior to C1D1. If possible, subjects must be in the recumbent position for a period of 5 minutes prior to the ECG. ECG should be conducted at C1D1, C2D1, D1 of every 4th cycle (i.e., C6, C10, C14, etc.), and at the Off-treatment visit. For high risk subjects (as defined in lenvatinib product label), conduct ECG in every cycle.
- h. An echocardiogram or MUGA scan is to be performed at Baseline, every 16 $\pm$ 2 weeks following first dose of study drug, and at the Off-Treatment visit, or sooner if clinically indicated. The Baseline ECHO/MUGA may be performed within 28 days prior to C1D1.
- i. Clinical chemistry and hematology results must be reviewed by the investigator prior to administration of study drug on C1D1 and within 48 hours after administering any study drug for all subsequent cycles. Electrolytes such as potassium, calcium, and magnesium should be monitored and abnormalities, when considered clinically significant, should be corrected in all participants before starting treatment. Scheduled assessments may be performed within 72 hours prior to the visit. If  $\geq$ Grade 3 hematologic or clinical chemistry toxicity, repeat laboratory test and AEs assessment at least every 3 days (until improvement to <Grade 3). TSH should be assessed for all subjects.
- j. Urine dipstick testing should be performed at Baseline, C1D15, C2D1, C2D15, and Day 1 of every subsequent cycle, or more frequently as clinically indicated, and at the Off-treatment Visit. For subjects with a history of proteinuria  $\geq$ 2+, urine dipstick testing should be performed until the results have been 1+ or negative for 2 treatment cycles. If a new event of proteinuria  $\geq$ 2+ occurs, refer to [Section 9.4.1.1.4](#) for further management guidelines. Urine glucose should be performed as part of the urine dipstick.
- k. A serum or urine pregnancy test will be performed at the Baseline Visit (or within 72 hours prior to the first dose of study medication), on Day 1 of each cycle from Cycle 2 onwards, and at the Off-treatment Visit in women of childbearing potential.
- l. Subjects on optional lenvatinib crossover treatment will continue to receive lenvatinib until disease progression, development of unacceptable toxicity, subject request, or withdrawal of consent, whichever occurs first. If the sponsor terminates the study, the sponsor will provide study drug(s) (outside of the study) for subjects who have not met the criteria for study drug discontinuation.
- m. All subjects who receive suspension formulation, with the exception of subjects using a nasogastric or gastrostomy tube, must complete the Palatability Questionnaire on C1D1 (or the subsequent visit). If the subject is unable to complete the questionnaire this must be done by their parents or their legal guardian.
- n. Prior to optional lenvatinib crossover, baseline tumor assessment must be re-established (i.e., new tumor assessment scans performed), unless the last assessment was performed within 4 weeks prior to Cycle 1 Day 1 of the crossover treatment. Tumor assessments may be performed as clinically indicated as per the institutional guidelines (but no less frequently than every 12 weeks), following the prevailing local standard of care. The scans will no longer be required to be sent to the ICL.
- o. Brain CT with contrast or MRI pre- and post- gadolinium contrast will be performed as clinically indicated as per the institutional guidelines, following the prevailing local standard of care.

- p. Height will be assessed at the Baseline Visit, Day 1 of every 4 cycles during treatment, at the Off-treatment Visit and every 3 months during the Post-treatment Follow-up. Assessment of height in Post-treatment Follow-up is not required once pubertal development is complete.
- q. Tanner Staging is only required for female subjects  $\geq 8$  years old, and male subjects  $\geq 9$  years old. Tanner Stage will be assessed at the Baseline Visit, at the Off-treatment Visit, and annually thereafter during the Post-treatment Follow-up. Tanner Staging is not required once pubertal development is complete (i.e. Tanner Stage 5).
- r. Survival data will be collected every 3 months for up to 2 years as per the protocol. All anticancer therapies will be collected.
- s. Concomitant medications will be recorded throughout the study and for 30 days after last dose. All anticancer therapy will be recorded until time of death or termination of Survival Follow-up.
- t. All AEs, including SAEs will be recorded from the date of signed informed consent, throughout the study, and for 30 days after last dose. SAEs irrespective of relationship to study treatment must be reported as soon as possible but not later than 24 hours.

#### 9.5.2.2 Description of Procedures/Assessments Schedule

Refer to [Table 5](#) for schedule and description of procedures in the Randomization Phase and [Table 6](#) for the Extension Phase.

#### 9.5.3 Appropriateness of Measurements

All clinical assessments are standard measurements commonly used in studies of relapsed or refractory solid tumors.

The safety assessments to be performed in this study, including hematology analyses, blood chemistry tests, urinalysis, radiologic studies, and assessment of AEs, are standard evaluations to ensure subject safety. The use of RECIST 1.1 for tumor assessments of solid tumors is widely accepted (see [Appendix 1](#)) ([Eisenhauer, et al., 2009](#)).

#### 9.5.4 Reporting of Serious Adverse Events, Pregnancy, and Events Associated with Special Situations

##### 9.5.4.1 Reporting of Serious Adverse Events

**All SERIOUS ADVERSE EVENTS, regardless of their relationship to study treatment, must be reported on a completed SAE form by email or fax as soon as possible but no later than 24 hours from the date the investigator becomes aware of the event.**

Serious adverse events, regardless of causality assessment, must be collected for 30 days after the subject's last dose. All SAEs must be followed to resolution or, if resolution is unlikely, to stabilization. Any SAE judged by the investigator to be related to the study treatment or any protocol-required procedure should be reported to the sponsor regardless of the length of time that has passed since study completion.

The detailed contact information for reporting of SAEs is provided in the Investigator Study File.

**For urgent safety issues**, please ensure all appropriate medical care is administered to the subject and contact the appropriate study team member listed in the Investigator Study File.

It is very important that the SAE report form be filled out as completely as possible at the time of the initial report. This includes the investigator's assessment of causality.

Any relevant follow-up information received on SAEs should be forwarded within 24 hours of its receipt. If the relevant follow-up information changes the investigator's assessment of causality, this should also be noted on the follow-up SAE form.

Preliminary SAE reports should be followed as soon as possible by detailed descriptions including copies of hospital case reports, autopsy reports, and other documents requested by the sponsor.

The investigator must notify his/her IRB/IEC of the occurrence of the SAE in writing, if required by their institution. A copy of this communication must be forwarded to the sponsor and/or the designated CRO monitor to be filed in the sponsor's Trial Master File.

#### 9.5.4.2 Reporting of Pregnancy and Exposure to Study Drug Through Breastfeeding

Any pregnancy in a female subject in which the estimated date of conception is either before the last visit or within 30 days of last study treatment, or any exposure to study drug through breastfeeding during study treatment or within 30 days of last study treatment, must be reported.

If an adverse outcome of a pregnancy is suspected to be related to study drug exposure, this should be reported regardless of the length of time that has passed since the exposure to study treatment.

A congenital anomaly, death during perinatal period, a spontaneous abortion or an induced abortion done due to safety concerns for either mother or fetus are considered to be an SAE and should be reported in the same time frame and in the same format as all other SAEs (see Reporting of Serious Adverse Events [Section 9.5.4.1]).

Pregnancies or exposure to study drug through breastfeeding must be reported by fax or email as soon as possible but no later than 24 hours from the date the investigator becomes aware of the pregnancy. The contact information for the reporting of pregnancies and exposure to study drug through breastfeeding is provided in the Investigator Study File. The Pregnancy Report Form must be used for reporting. All pregnancies must be followed to outcome. The outcome of the pregnancy must be reported as soon as possible but no later than 24 hours from the date the investigator becomes aware of the outcome.

A subject who becomes pregnant must be withdrawn from the study.

#### 9.5.4.3 Reporting of Events Associated with Special Situations

##### 9.5.4.3.1 REPORTING OF ADVERSE EVENTS ASSOCIATED WITH STUDY DRUG OVERDOSE, MISUSE, ABUSE, OR MEDICATION ERROR

Adverse events associated with study drug overdose, misuse, abuse, and medication error refer to AEs associated with uses of the study drug outside of that specified by the protocol. Overdose, misuse, abuse, and medication error are defined as follows:

Overdose	Accidental or intentional use of the study drug in an amount higher than the protocol-defined dose
Misuse	Intentional and inappropriate use of study drug not in accordance with the protocol
Abuse	Sporadic or persistent intentional excessive use of study drug accompanied by harmful physical or psychological effects

---

Medication error	Any unintentional event that causes or leads to inappropriate study drug use or subject harm while the study drug is in the control of site personnel or the subject.
------------------	---

All AEs associated with overdose, misuse, abuse, or medication error should be captured on the Adverse Event CRF and also reported using the procedures detailed in Reporting of Serious Adverse Events ([Section 9.5.4.1](#)) even if the AEs do not meet serious criteria. Abuse and Intentional Overdose, even if asymptomatic, are always to be captured as an AE. If the AE associated with an overdose, misuse, abuse, or medication error does not meet serious criteria, it must still be reported using the SAE form and in an expedited manner but should be noted as nonserious on the SAE form and the Adverse Event CRF.

#### 9.5.4.3.2 REPORTING OF ABNORMAL HEPATIC TESTS OF CLINICAL INTEREST

The following combination of abnormal laboratory tests\*, as determined by way of protocol-specified laboratory testing or unscheduled laboratory testing and whether nonserious or serious, should be entered on the Adverse Event CRF and reported using the procedures detailed in Reporting of Serious Adverse Events ([Section 9.5.4.1](#)). If the event does not meet serious criteria, the seriousness criteria on the SAE form should be indicated as “nonserious.”

- Elevated AST or ALT lab value that is greater than or equal to  $3\times$  the upper limit of normal  
AND
- Elevated total bilirubin lab value that is greater than or equal to  $2\times$  the upper limit of normal  
AND AT THE SAME TIME
- Alkaline phosphatase lab value that is less than  $2\times$  the upper limit of normal

\*Note: These criteria are based upon available regulatory guidance documents. The purpose of the criteria is to specify a threshold of abnormal hepatic tests that may require additional evaluation for an underlying etiology. In addition to reporting the abnormal hepatic laboratory tests on a SAE form, the site should also consult the medical monitor for guidance on assessment and follow-up. At a minimum, laboratory testing should be repeated at least once weekly until improvement or identification of a cause unrelated to study drug use that is unlikely to improve.

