### 9.3.1 Inclusion Criteria

Subjects must meet all of the following criteria to be included in this study:

1. Histologically or cytologically confirmed diagnosis of high grade osteosarcoma.
2. Refractory or relapsed osteosarcoma after 1 to 2 prior lines of systemic treatments.
3. Measurable or evaluable disease per RECIST 1.1 that meets the following criteria:
  - Measurable disease is defined as a lesion with a minimum size (by long axis) of 10 mm using computed tomography/magnetic resonance imaging (CT/MRI) (lymph nodes must be accurately measurable with a minimum size [by short axis] of 15 mm).
  - Lesions that have had external beam radiotherapy (EBRT) or locoregional therapies such as radiofrequency (RF) ablation must have subsequently grown unequivocally to be deemed a target lesion.
  - Any other non-measurable lesions will be considered evaluable disease.
4. Aged 2 years to  $\leq 25$  years at the time of informed consent.
5. Life expectancy of 12 weeks or more.
6. Lansky play score  $\geq 50\%$  or Karnofsky Performance Status score  $\geq 50\%$ . Use Karnofsky for subjects  $\geq 16$  years of age and Lansky for subjects <16 years of age. Subjects who are unable to walk because of paralysis, but who are able to perform ADL while wheelchair bound, will be considered ambulatory for the purpose of assessing the performance score.
7. Adequate bone marrow function as evidenced by:
  - a. absolute neutrophil count (ANC)  $\geq 1.5 \times 10^9/L$ .  
(subjects with bone marrow involvement should have ANC  $\geq 0.8 \times 10^9/L$  and leucocyte count  $\geq 1 \times 10^9/L$ ).
  - b. hemoglobin  $\geq 8.0 \text{ g/dL}$  (a hemoglobin of  $< 8.0 \text{ g/dL}$  is acceptable if it is corrected by growth factor or transfusion before Cycle 1 Day 1).
  - c. platelet count  $\geq 100 \times 10^9/L$ .
8. Adequate blood coagulation function defined by International Normalized ratio or prothrombin time (INR/PT) and activated partial thromboplastin time or partial thromboplastin time (aPTT/PTT)  $\leq 1.5$  unless participant is receiving anticoagulant therapy, as long as INR/PT and aPTT/PTT are within therapeutic range of intended use of anticoagulants.
9. Adequate liver function as evidenced by:
  - a. Bilirubin  $\leq 1.5$  times the upper limit of normal (ULN).
  - b. Alanine aminotransferase (ALT), and aspartate aminotransferase (AST)  $\leq 3 \times \text{ULN}$  (in the case of liver metastases  $\leq 5 \times \text{ULN}$ ).

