#### 9.4.9 Drug Supplies and Accountability

In compliance with local regulatory requirements, drug supplies will not be sent to the investigator until the following documentation has been received by the sponsor:

- A signed and dated confidentiality agreement
- A copy of the final protocol signature page, signed and dated by both the sponsor and investigator
- Written proof of approval of the protocol, the ICFs, and any other information provided to the subjects by the IRB/IEC for the institution where the study is to be conducted
- A copy of the IRB/IEC-approved ICF and any other documentation provided to the subjects to be used in this study
- The IRB/IEC membership list and statutes or Health and Human Services Assurance number

- A copy of the certification and a table of the normal laboratory ranges for the reference laboratory conducting the clinical laboratory tests required by this protocol
- An investigator-signed and dated FDA Form FDA 1572, or a completed Investigator and Site Information Form
- Financial Disclosure form(s) for the principal investigator (PI) and all subinvestigators listed on Form FDA 1572 or Investigator and Site Information Form
- A signed and dated curriculum vitae (CV) of the PI including a copy of the PI's current medical license or medical registration number on the CV
- A signed and dated clinical studies agreement
- A copy of the regulatory authority approval for the country in which the study is being conducted (if required), and the Import License (if required)

The investigator, study staff, and the designated pharmacist will be responsible for the accountability of all study drugs/study supplies (dispensing, inventory, and record keeping) following the sponsor's instructions and adherence to GCP guidelines as well as local or regional requirements.

Under no circumstances will the investigator allow the study drugs to be used other than as directed by this protocol. Study drugs will not be dispensed to any individual who is not enrolled in the study other than the parent, guardian, or authorized legal representative of a study subject.

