**Table 4 Clinical Laboratory Tests**

Category	Parameters
Hematology	Hematocrit, hemoglobin, platelets, RBC count, and WBC count with differential (bands, basophils, eosinophils, lymphocytes, monocytes, neutrophils)
Chemistry	
Electrolytes a	Bicarbonate, chloride, potassium, sodium, calcium, magnesium, phosphorus
Liver function tests	ALT, alkaline phosphatase, AST, conjugated (direct) bilirubin b , total bilirubin, INR/PT, aPTT/PTT c
Renal function tests	BUN or urea, creatinine
Other chemistries	Albumin, amylase, glucose, LDH, lipase, total protein
Thyroid function tests d	Thyroid stimulating hormone, free T4 level
Urinalysis for microscopy e	RBCs
Urine dipstick testing e,f	Blood, protein, glucose
Other g	Pregnancy test (serum or urine $\beta$ -hCG)

ALT = alanine aminotransferase, aPTT = activated partial thromboplastin time, AST = aspartate aminotransferase, BUN = blood urea nitrogen,  $\beta$  hCG = beta-human chorionic gonadotropin, INR = International Normalized ratio, LDH = lactate dehydrogenase, aPTT = activated partial thromboplastin time, RBC = red blood cells, T4 = thyroxine, TSH = thyroid stimulating hormone, WBC = white blood cells.

- a. Electrolytes such as potassium, calcium, and magnesium should be monitored and abnormalities, when considered clinically significant, should be corrected in all participants before starting treatment.
- b. Direct bilirubin should be assessed if total bilirubin is elevated.
- c. INR/PT and aPTT/PTT should only be performed as part of the screening assessment. During the study, INR/PT and aPTT/PTT should be performed if clinically indicated.
- d. Thyroid function will be assessed every 2 cycles for all subjects.
- e. If urine dipstick testing suggests a urinary tract infection, or if clinically indicated, a urine microscopy, culture, and sensitivity should be performed at the institution's laboratory
- f. If urine protein is  $\geq 2+$ , then a spot test for protein-creatinine ratio and if possible, a 24-hour urine collection should be done to quantify the 24 hour urine protein excretion.
- g. For sites in Germany: HIV and Hepatitis B/C tests are required during Screening.

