All clinical laboratory tests during the study will be performed at qualified local laboratories. All hematology, blood chemistry (including pregnancy test, as applicable), and urinalysis samples are to be obtained prior to study drug administration and sent to the local laboratory on the day of collection unless otherwise instructed.

Clinical chemistry and hematology results must be reviewed prior to administration of study drug on Cycle 1 Day 1 and within 48 hours after dispensing study drug for all subsequent cycles. Electrolytes such as potassium, calcium, and magnesium should be monitored and

abnormalities, when considered clinically significant, should be corrected in all participants before starting treatment. Scheduled assessments may be performed within 72 hours prior to the visit. If  $\geq$  Grade 3 hematologic or clinical chemistry toxicity, repeat laboratory test and AEs assessment at least every 3 days (until improvement to  $<$  Grade 3). Refer to [Table 1](#) (study drug dose reduction and interruption instructions) for the management of clinically significant laboratory abnormalities. Every effort should be made to collect samples for analysis at the local laboratory at the same time.

A laboratory abnormality may meet the criteria to qualify as an AE as described in this protocol (see [Section 9.5.1.4.1](#) and the CRF Completion Guidelines. In these instances, the AE corresponding to the laboratory abnormality will be recorded on the Adverse Event CRF (see [Section 9.5.4.3.2](#)).

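### The special hepatic report requires ALP below 2×ULN with no allowance for ALP already raised at entry, so some nonserious transaminase-plus-bilirubin cases in this osteosarcoma population cannot trigger it

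*Protocol*

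**What the plan says.** Section 9.5.4.3.2 sets three conditions joined by AND: AST or ALT at least 3×ULN, total bilirubin at least 2×ULN and, simultaneously, "Alkaline phosphatase lab value that is less than" 2×ULN. When all three hold, the site enters the finding on the Adverse Event CRF and reports it through the SAE procedure, marked nonserious if it is not serious. Two further actions follow: "the site should also consult the medical monitor for guidance on assessment and follow-up", and "At a minimum, laboratory testing should be repeated at least once weekly until improvement" or until an unrelated cause that is unlikely to improve is found. The section's note says the criteria rest on regulatory guidance and are meant to flag abnormalities that may need an etiology work-up.

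Three other places bear on the ALP limb:

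- **Section 9.3.1.** Criterion 1 requires high-grade osteosarcoma. Criterion 9, "Adequate liver function as evidenced by" two items, limits bilirubin and ALT/AST (with a wider ALT/AST limit for liver metastases). It sets no limit on ALP.
- **Table 4.** The liver tests include "ALT, alkaline phosphatase, AST, conjugated (direct) bilirubin". No bone isoenzyme or GGT is listed. Note b adds: "Direct bilirubin should be assessed if total bilirubin is elevated".
- **Sections 9.4.9 and 9.5.1.4.3.** Sites supply "a table of the normal laboratory ranges for the reference laboratory conducting the clinical laboratory tests", and "All clinical laboratory tests during the study will be performed at qualified local laboratories". ULN therefore means the local laboratory's limit.

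**The concern.** An ALP ceiling in a rule of this kind is normally there to set aside cholestatic patterns; the protocol does not state its purpose. That works only if a high ALP points to the liver or bile ducts. Every subject here has a malignant bone tumor. If bone disease can raise total ALP, which is general medical knowledge and not stated in the protocol, a high value need not mean cholestasis, and no listed test separates the sources.

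A subject can also enter the trial with ALP at or above 2×ULN. While it stays there, no combination of transaminase and bilirubin values meets the trigger.

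What is at stake is case-level safety review: a child or young adult with concurrent transaminase and bilirubin elevation would not automatically come to the medical monitor's attention.

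**Working it through.** **Step 1: apply the rule as written.** The report is due if (AST or ALT ≥3×ULN) AND (total bilirubin ≥2×ULN) AND (ALP <2×ULN).

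| AST or ALT | Total bilirubin | ALP | Special report |
|---|---|---|---|
| ≥3×ULN | ≥2×ULN | <2×ULN | yes |
| ≥3×ULN | ≥2×ULN | ≥2×ULN, any source, any baseline | no |

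Nothing elsewhere in Amendment 02 gives an exception for the second row.

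**Step 2: can a subject be in the second row from entry?** Yes. Criterion 9 leaves ALP free, so baseline ALP ≥2×ULN does not bar enrollment.

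**Step 3: what still applies in the second row.**

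- *Serious cases.* Sections 9.5.1.4.2 and 9.5.4.1 require reporting within 24 hours. The investigator may also judge a case an important medical event and so make it serious.
- *Grade 3 or higher chemistry.* Section 9.5.1.4.3 requires a repeat test and AE assessment at least every 3 days.
- *Liver tests between visits.* Section 9.4.1.1.5 asks for liver function testing on schedule and as clinically indicated. If there are signs or symptoms of liver injury, it adds Table 1 dose management and close monitoring.
- *AE recording and follow-up.* Under section 9.5.1.4.1 a laboratory result is an AE if it leads to intervention, withholding or withdrawal; otherwise the investigator judges. Recorded AEs are followed.
- *Aggregate review.* The IDMC safety reviews (section 9.7.3) and the laboratory shift tables (section 9.7.1.8.3) do not depend on the trigger.

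This leaves the nonserious case, mainly below Grade 3. For Grade 1 or tolerable Grade 2, Table 1 continues lenvatinib unchanged. Such a case loses the automatic AE entry, the SAE-form report, the prompted consultation and the fixed weekly minimum.

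**Step 4: size of the weekly minimum.** Scheduled chemistry (Table 5; Appendix 11 blood sampling schedule, note a) is at baseline, C1D15, C2D1, C2D15, then Day 1 of each 21-day cycle. Count C1D1 as day 1 and take baseline as day 1. Guaranteed weekly tests strictly between two scheduled tests = interval/7 − 1.

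| Interval | Days | Extra weekly tests |
|---|---|---|
| Baseline to C1D15 | 15 − 1 = 14 | 14/7 − 1 = 1 |
| C1D15 to C2D1 | 22 − 15 = 7 | 7/7 − 1 = 0 |
| C2D1 to C2D15 | 36 − 22 = 14 | 14/7 − 1 = 1 |
| C2D15 to C3D1 | 43 − 36 = 7 | 7/7 − 1 = 0 |
| C3D1 to C4D1, and each later cycle | 64 − 43 = 21 | 21/7 − 1 = 2 |

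From Cycle 3 the rule would guarantee up to 2 interim tests per cycle. In Arm B this covers Cycles 3 to 5 at most, because those subjects are off treatment after 5 cycles unless they cross over.

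**Step 5: number of cases.** The protocol gives no ALP distribution and no expected rate of combined elevations. The only available bounds are uninformative: 0 and the 72 planned subjects. If local ranges are age-specific, they may already absorb growth-related ALP, leaving only what the tumor adds.

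**The case against.** The three-part criterion is a deliberate choice that the protocol attributes to regulatory guidance, and the text is neither contradictory nor unworkable. It sets a minimum trigger and does not stop a site from calling the medical monitor or retesting in any other case. The harm depends on a link between osteosarcoma and ALP that the documents do not state or quantify. Dropping the ALP limb altogether would also bring in true cholestasis and metastatic liver disease.

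Much of this stands. The link is an assumption, and the number of cases may be zero. A reader might infer that up to two tests per cycle are actually lost, or that these liver cases go unseen. The documents do not support either reading: clinically indicated testing, AE follow-up and the investigator's freedom to classify a case as serious all remain. What goes is the guaranteed minimum, not the tests. It would also be wrong to ask for a waiver when ALP is judged to be of bone origin, because none of the listed tests identifies the source.

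One part does not stand. Citing general guidance does not adapt the rule to a population in which all subjects have bone tumors and entry leaves ALP unrestricted. The rule's stated purpose is to prompt an etiology work-up, and it already lets weekly testing end once an unrelated cause is found. Excluding cases on ALP beforehand pre-empts that step.

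**Conclusion.** The point holds as a minor, cheap improvement. As written, a subject with ALP at or above 2×ULN at baseline cannot meet the trigger for as long as ALP stays there, whatever AST, ALT and bilirubin do. That follows from the text alone. That the ALP limb is a poor screen for cholestasis in this trial rests on the assumption that bone disease can raise total ALP.

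The loss per case is the automatic AE entry and SAE-form report, one prompted consultation and the guaranteed weekly retest, in nonserious cases that are mainly below Grade 3.

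A reader might go further and infer that most subjects are outside the rule, or that serious liver injury would go unreported. The documents give no ALP data for the first, and SAE reporting does not depend on ALP, which rules out the second. No efficacy conclusion, dosing rule or stopping rule is affected.

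**What to change.** In section 9.5.4.3.2, state that the ALP limit does not apply when the subject's ALP was above ULN at baseline. Alternatively, apply the report, consultation and weekly retest to AST or ALT ≥3×ULN with total bilirubin ≥2×ULN regardless of ALP. The first option adds fewer reports; the second also covers ALP that rises after entry. Under either, record baseline ALP, current ALP and direct bilirubin on the form to help the medical monitor weigh cholestasis or liver metastasis.

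The cost is one line of text and three form values, all from tests already scheduled or recommended in Table 4. The downside is a few extra nonserious reports, some of which will prove to be cholestasis or liver metastasis.
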